### **I. Collection of baseline data**

[figure not shown]
All study participants met with a research assistant (RA) at their primary care clinic. The research assistant administered the Patient Baseline Survey (see Attachments) either in English or in Spanish, based on the patient's preference. The RA also administered spirometry (see Attachments) the 6-minute walk test (see Attachments), and recorded weight, height, blood pressure, pulse and O2.

### **J. Randomization**

A random binary sequence, stratified by site, was used to order study arm assignment into sequentially numbered envelopes. Once baseline measures are complete, the research

assistant asked the patient to open a sealed envelope with a randomization card indicating whether the patient will be assigned to the usual care or health coaching arm.

## CONSORT Diagram for AIR Health Coaching Study for COPD

### K. Outcomes

Study outcomes and references for the measures are shown in Table 1 below. All outcomes were measured at baseline and 9 months. Additional phone surveys at 3 and 6 months ask about smoking status, COPD-related quality of life (CRQ-SF) and bed days in past 4 weeks due to COPD. The 3 and 6 month surveys also asked about any ED visits or hospitalization at sites other than the county hospital. Medical records were then requested for these visits. Participants

receive \$10 for each measure (survey, exercise capacity test, and spirometry) at baseline, \$10 for each survey at 3 and 6 months, and \$20 for each measure completed at 9 months in acknowledgement of their participation in the study.

**COPD-related quality of life** (Specific Aim 1) was The Chronic Respiratory Disease Questionnaire (CRQ) which generates scores in four domains (dyspnea, fatigue, physical function and mastery) and an overall score, has been validated in multiple studies. The CRQ has the advantage of having a near normal total score distribution and of being sensitive to change. and has establish minimal clinically important differences for total score and for each of its 4 domain scores (dyspnea, fatigue, physical function and mastery) We chose to use the standardized, self-administered version of the CRQ due to its ease of administration and superior discriminant validity.

**A COPD exacerbation** (Specific Aim 2) was defined as worsening of respiratory symptoms resulting in prescription of an antibiotic and/or steroid medication, an unscheduled or emergency visit, or a hospitalization. Similar utilization-based definitions have been used in previous studies for moderate to severe exacerbations and is consistent with guideline definition.

**Exercise capacity** (Specific Aim 3) was measured by the standardized 6 minute walk test (6MWT) which measures how far a patient can walk in 6 minutes, was administered by the RA using an established protocol recommended by the American Thoracic Society. The distance a patient is able to walk in 6 minutes, is a well-recognized and widely used measure of exercise capacity. The MICD for the 6MWT is generally considered to be 25 to 50 meters. Previous studies have documented the 6MWT is sensitive to measuring change over time.

**Self-efficacy** (Specific Aim 4) has been shown to predict functional capacity and quality of life for patients with COPD. We chose to measure self-efficacy using the 6 item scale developed by [name] and others at Stanford.

Patient-reported **quality of care** was measured using the short form of the Patient Assessment of Chronic Illness Care (PACIC)

Level of **COPD symptoms** was assessed using the COPD Assessment Test (CAT).

**Lung Function** was assessed by spirometry conducted by the research assistant using the VMAX Vyntus SPIRO with SentrySuite. All spirometry results were reviewed by the Director of the Community Spirometry program to determine quality based on American Thoracic Society (ATS) guidelines. To be used, spirometry had to receive a grade of C or higher. Patients were allowed a maximum of 10 attempts at either pre- or post-bronchodilator spirometry. If a patient felt unable to complete the test, the RA terminated the attempt and referred the patient to the pulmonary function testing (PFT) lab or to a respiratory therapist for testing.

**Smoking status** was ascertained by patient self-report. Patients who reported having smoking at all in the past 30 days were considered to be current smokers.

Patient-reported **medication adherence** was assessed using the Morisky Medical Adherence Scale (MMAS4)

**COPD knowledge** was assessed using 10 questions developed for the current study.

**Inhaler use** was observed by research assistants and documented using checklists specific to each type of inhaler (see Attachments). Checklists were based on published checklists and consistent with manufacturers' directions for inhaler use.

**Symptoms of depression** in the previous 4 weeks was measured using the Patient Health Questionnaire 8-item version (omitting the question asking about suicidal ideation).

**Functional status** was measured by patient-self report of number of days unable to do usual activities due to COPD (bed days).

**Utilization** was assessed at the end of the study by review of EMR and of all records obtained from outside hospitals.

**Guideline concordant care** included prescription for COPD medication corresponding to GOLD recommendation by COPD category (A=low symptoms, low risk; B=high symptoms, low risk, C=low symptoms, high risk and D=high symptoms, high risk).

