### M. Sample size

The original target sample size for enrollment was 250 patients allocated in a 1:1 ratio between study arms. Sample size and power estimates for comparison of the health-coached and usual care groups assumed a target power of .80 or higher and significance to be defined by a two-sided  $\alpha = 0.05$ . Expected effect sizes and minimum clinically important differences (MCIDs) for each outcome, were derived from previous studies for the primary measures for the first 3 aims: COPD-related quality of life, number of exacerbations, and the 6-minute walk test. Expected differences and minimal clinically important differences were not available for the fourth specific aim, patient self-efficacy of COPD management. Based on our previous experience in conducting randomized controlled trials in this population, (Willard Grace) we assumed an attrition rate of 20%, resulting in 200 patients available for analysis at the end of the study. We further assumed an intraclass correlation coefficient (ICC) of 1% between clinic sites based on our previous experience. The target sample size gave us sufficient power to detect the anticipated differences between groups for each outcome variable, which are at least as large as the MCIDs previously established, as shown in the following table.

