**Table 2. Original study power based on 100 participants in each arm at end of study**

Outcome	MCID*	Power of study to detect MCID	Difference expected based on previous studies	Minimum difference for which study has >80% power
CRQ-SF total	1.0	.99	.73-2.00	0.33
CRQ-SF dyspnea	0.5	.88	.76-1.06	0.45
# of exacerbations	22%	.90	20-26%	20%
6 minute walk test	50 m	.97	48-85 m	25 m

As detailed in section F18 below, we were not able to meet our initial goal of 250 patients and had modify our enrollment goal to 190 patients that, with a 20% attrition, was expected to yield 152 patients at the end of the study. The power for the revised sample size is presented below.

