**Table 3. Revised study power based on 76 participants in each arm at end of study**

Outcome	MCID*	Power of study to detect MCID	Difference expected based on previous studies	Minimum difference for which study has >80% power
CRQ-SF total	1.0	.96	.73-2.00	0.45
CRQ-SF dyspnea	0.5	.78	.76-1.06	0.51
# of exacerbations	22%	.81	20-26%	22%
6 minute walk test	50 m	.92	48-85 m	35 m

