Statistical Analysis Plan
Aides in Respiration (AIR) Health Coaching for Patients with COPD

NCT02234284

Updated September 8, 2014

Uploaded March 7, 2019

Baseline participant characteristics were compared between study arms and tested for significance using chi-square for categorical variables, t-tests for normally distributed continuous variables, and appropriate non-parametric tests for non-normally distributed continuous variables. Outcomes were compared by group assignment (intention to treat) using generalized linear mixed models (GLMMs) with a normal distribution and identity link for continuous outcomes and Poisson distribution with a log link for count outcomes. GLMMs uses random effects to account for within-participant correlations, nested random effects to account for clustering, and accommodate missing data under the assumption that the outcomes are missing at random.¹⁻⁵ In all models, baseline levels of the outcome were entered as a predictor and follow-up levels as the dependent variable, with a nested random effect of practice site to account for clustering. Hypothesis tests were 2-sided with p-values<0.05 considered statistically significant. Models used available data, while sensitivity analyses were conducted repeating primary analyses with multiple imputation procedures. Additional, exploratory per protocol and sub-group analyses were also performed, limiting patients in the coached arm to those receiving at least half of the protocol target for contacts. Differential effects (effect modification) was examined for 3 pre-specified subgroups: English vs Spanish as primary language; current smokers vs other; and COPD classification GOLD category D (high symptoms and high risk) vs other.

O. References

1. Fairclough D. Design and analysis of quality of life studies in clinical trials. New York: Chapman & Hall/CRC; 2002.
2. Little RJ and Rubin DB. Statistical analysis with missing data. New York, Wiley, 1987

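### The CRQ-SF total rows of Tables 2 and 3 are internally inconsistent: the MCID of 1.0, the printed powers and the detectable differences cannot all be right

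*Protocol*

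**What the plan says.** The CRQ-SF total and its dyspnea sub-scale are the two primary outcomes (protocol Section A, Specific Aim 1, and Table 1). Section K says that the CRQ "has establish minimal clinically important differences for total score and for each of its 4 domain scores", without giving a value, an SD or the scoring rule for the total.

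The numbers are in Section M. The columns of Tables 2 and 3 are, in order, MCID, power at the MCID, expected difference, and smallest difference with more than 80% power:

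- Table 2, 100 per arm: "CRQ-SF total 1.0 .99 .73-2.00 0.33" and "CRQ-SF dyspnea 0.5 .88 .76-1.06 0.45".
- Table 3, 76 per arm: "CRQ-SF total 1.0 .96 .73-2.00 0.45". The dyspnea entries there are MCID 0.5, power .78, expected .76 to 1.06, and smallest difference 0.51.

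Section M also states that the anticipated differences are no smaller than the established MCIDs. No SD is given for any outcome. The SAP gives a significance rule ("Hypothesis tests were 2-sided with p-values<0.05 considered statistically significant") and does not mention MCIDs.

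**The concern.** For a comparison of two means, the power at a given difference and the difference detectable with 80% power both follow from the same SD and sample size. Once one is printed, the other is fixed. In the total row, a detectable difference of 0.33 or 0.45 lies so far below 1.0 that power at 1.0 should be practically 1, yet Table 3 prints .96. The detectable difference also grows by more than a third between the tables, which a change from 100 to 76 per arm cannot produce.

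These rows are the stated justification for the revised sample size on a primary outcome. The two ways of making the powers coherent imply SDs that differ by a factor of two (0.83 or 1.65). A reader therefore cannot tell whether the trial could detect about 0.4 or only about 0.75 on this score. Under the larger SD, the smallest detectable difference with 76 per arm (0.76) would lie just above the low end of the expected range (.73).

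**Working it through.** **Inputs.** Section M "assumed a target power of .80 or higher and significance to be defined by a two-sided" alpha of 0.05. Analysed numbers: "The original target sample size for enrollment was 250 patients allocated in a 1:1 ratio between study arms", and "we assumed an attrition rate of 20%, resulting in 200 patients available for analysis at the end of the study", so 250 × 0.80 = 200, or 100 per arm. The revised figure is 190 × 0.80 = 152, or 76 per arm. The row entries are those quoted above. No SD is given, so it is solved from the table.

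**Formulas** (two arms of n, normal approximation):

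- SE = SD × √(2/n), with √(2/100) = 0.1414 and √(2/76) = 0.1622.
- Difference with 80% power = (1.960 + 0.842) × SE = 2.802 × SE.
- Power at difference d = Φ(d/SE − 1.960).

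**1. Check on a row that works.** Dyspnea, Table 2: SD = 0.45/(2.802 × 0.1414) = 1.136, and power at 0.5 = .876 (printed .88). Table 3: SD = 0.51/(2.802 × 0.1622) = 1.122, and power at 0.5 = .784 (printed .78). The method reproduces the plan's figures.

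**2. Total score, SD from the detectable difference.**

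- Table 2: SD = 0.33/(2.802 × 0.1414) = 0.833. Power at 1.0: 1.0/(0.833 × 0.1414) − 1.960 = 6.5, so above .9999 (printed .99).
- Table 3: SD = 0.45/(2.802 × 0.1622) = 0.990. Power at 1.0: 1.0/(0.990 × 0.1622) − 1.960 = 4.3, so above .9999 (printed .96).

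A printed .99 could be a loose way of writing a power near 1, so Table 2 alone does not rule out 1.0. Table 3's .96 does.

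**3. Scaling between tables.** With one SD, the detectable difference grows by √(100/76) = 1.147. Then 0.33 × 1.147 = 0.379 (0.373 to 0.384 allowing for rounding of 0.33), not 0.45. The printed ratio is 0.45/0.33 = 1.36. For dyspnea it is 0.51/0.45 = 1.13, as expected.

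**4. What the printed powers do fit.**

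| Reading | 100 per arm | 76 per arm | Which printed entries fail |
|---|---|---|---|
| Difference 0.5, SD 0.833 | power .989 | power .959 | the 1.0 label; Table 3's 0.45 |
| Difference 0.5, Table 3's own SD 0.990 | n/a | power .876 | Table 3's .96 |
| Difference 1.0, SD solved from printed power | SD 1.650, detectable 0.654 | SD 1.661, detectable 0.755 | 0.33 and 0.45 |

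The SDs in the last row are 1.0/[(1.960 + 2.326) × 0.1414] and 1.0/[(1.960 + 1.751) × 0.1622].

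**5. Variants.** A t-test in place of the normal approximation, a one-sided test, and rounding of the detectable differences all leave power at 1.0 above .999. Section M's intraclass correlation of 1% over seven sites gives a design effect of 1 + (152/7 − 1) × 0.01 = 1.21. Applied to power only, the harshest choice, it still leaves .9999 at 76 per arm. Reaching .96 would need an inflation of about 2.8.

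**6. Expected range.** The low end for the total is .73, below 1.0, which contradicts Section M's statement about anticipated differences. The walk test (48 against 50 m) and exacerbations (20% against 22%) also fall short, by less.

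**7. Six-minute walk row.** The detectable differences of 25 and 35 m imply SDs of 63.1 and 77.0 m. Power at 50 m is then above .999 and .979, against the printed .97 and .92. The printed powers at 50 m instead fit one SD of about 92 m in both tables.

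**The case against.** It is tempting to go further and say that the total's MCID is simply a misprint for 0.5. The case for this has substance. Both printed powers match 0.5 to two decimals under Table 2's SD. The SD implied for the total (0.83 to 0.99) is smaller than dyspnea's (about 1.13), as for an average of domains and not a sum. On an average scale, a gain of 0.5 in every domain is a gain of 0.5 in the total. The .73 lower bound would then clear the MCID. A reader might also infer that a benefit between 0.5 and 1.0 would be dismissed on the total but accepted on dyspnea.

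The documents do not carry that reading:

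- The match to .96 needs Table 2's SD. Table 3's own 0.45 gives .876.
- An MCID of 1.0 with .99 and .96 fits a single SD of about 1.65 across both tables, so the MCID and power columns agree with each other. It is the detectable differences that do not scale. The walk test shows the same pattern, which points at that column at least as plausibly.
- The argument that the total is an average depends on the suspect column. With SD 1.65, the total would vary more than dyspnea. The scoring scale is never stated, and different MCIDs conflict only if the scales are the same.
- Section K does not say that the MCIDs are equal, and the SAP sets no interpretation rule based on them.

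It can also be said that the practical effect is small. That largely stands: no test, decision rule or enrolment figure depends on the correction, and if SD 0.83 is right, power at 1.0 is understated. It does not make the rows coherent.

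**Conclusion.** The point holds as an inconsistency within the CRQ-SF total rows of Tables 2 and 3, with the wrong column left open. At the SDs implied by the detectable differences, power at 1.0 is above .9999, not .99 and .96, and 0.33 at 100 per arm corresponds to about 0.38 at 76 per arm, not 0.45. Depending on which entries are right, the detectable difference with 76 per arm is about 0.38 or about 0.76. Section M's statement that anticipated differences reach the MCIDs is also wrong for the total if 1.0 is kept.

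This assumes a two-sided comparison of two means with one SD for both tables, an approach that reproduces the dyspnea row. The documents do not support concluding that 0.5 is the correct MCID for the total, or that the plan judges the two primary scores by conflicting thresholds.

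**What to change.** In Section M, state how the CRQ-SF total is scored (item mean or sum), the SD assumed, and the source of its MCID. Then recompute the power and detectable-difference entries in both tables from that single SD.

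- If the SD is 0.83: restate Table 3's detectable difference as about 0.38, and either show power at 1.0 as >.99 in both tables or relabel .99 and .96 as power at 0.5.
- If the SD is 1.65: restate the detectable differences as about 0.65 and 0.76.

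Before changing the MCID, confirm from its source whether it is on the same scale as dyspnea's 0.5. If 1.0 is kept, correct the Section M statement that anticipated differences are at least as large as the MCIDs. Recheck the six-minute walk row in the same pass.

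The cost is table entries and wording only, with no added patients, data or analyses.

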**Table 1. Outcomes with reference to specific aim (SA) if relevant**

Outcomes	Measure used	Source	Reference
Primary (SA 1)			
COPD-related quality of life	Short Form Chronic Respiratory Disease Questionnaire (SF-CRQ)	Patient survey	1-10
Dyspnea	SF-CRQ dyspnea sub-scale	Patient survey	1-10
Secondary outcomes			
COPD exacerbations (SA 2)	Review of medical records		11
Exercise capacity (SA 3)	6 Minute Walk Test	Administered by RA	12-16
Self-efficacy for managing COPD (SA 4)	Stanford Self-Efficacy for Managing Chronic Disease	Patient survey	17
Other pre-specified outcomes			
Patient-reported quality of care	Patient Assessment of Chronic Illness Care (PACIC)	Patient survey	18
COPD symptoms	COPD Assessment Test (CAT)	Patient survey	19-21
Lung function	Force Expiratory Volume at 1 second (FEV1) by spirometry	Administered by RA	
Smoking status	Smoked cigarette in past 30 days	Patient survey	NA
Medication adherence	Morisky Medication Adherence Scale	Patient survey	22,23
Knowledge of COPD	Individual questions	Patient survey	NA
Correct use of inhalers	Inhaler checklist for each type of inhaler (adapted)	Observed by RA	24-26

Functional status	Bed days due to respiratory problems	Patient survey	27, 28
Utilization by type of visit	Outpatient, urgent care, emergency department and hospitalizations	Review of EMR	NA
Post-hoc outcomes			
Symptoms of depression	Patient Health Questionnaire (PHQ-8)		29
Guideline concordant care	GOLD recommendations	Patient-report and review of EMR	5

### L. Follow-up

Participant contact information, including phone numbers, address and emails, were obtained at enrollment the best way(s) to contact the participant was established. Participants in both study arms were contacted every 3 months by the RA and asked to complete a brief interval survey (see attachments) which asked about recent exacerbations, and current smoking status. Participants were paid \$10 for each interval survey. To the extent possible, the same RA follow-up with participant each time to help build trust. For the 9-month, end of study measures, which required an in person visit, RAs met with the patient at the patients primary care clinic, helping to arrange transportation if needed. The proportion of patients completing surveys were similar between study arms at 3 and 6 months, was but higher in usual care arm at 9 months. Reasons for withdrawal from the study was documented to the extent possible, based on contacting the patient and reviewing the medical record.

### M. Sample size

The original target sample size for enrollment was 250 patients allocated in a 1:1 ratio between study arms. Sample size and power estimates for comparison of the health-coached and usual care groups assumed a target power of .80 or higher and significance to be defined by a two-sided  $\alpha = 0.05$ . Expected effect sizes and minimum clinically important differences (MCIDs) for each outcome, were derived from previous studies for the primary measures for the first 3 aims: COPD-related quality of life, number of exacerbations, and the 6-minute walk test. Expected differences and minimal clinically important differences were not available for the fourth specific aim, patient self-efficacy of COPD management. Based on our previous experience in conducting randomized controlled trials in this population, (Willard Grace) we assumed an attrition rate of 20%, resulting in 200 patients available for analysis at the end of the study. We further assumed an intraclass correlation coefficient (ICC) of 1% between clinic sites based on our previous experience. The target sample size gave us sufficient power to detect the anticipated differences between groups for each outcome variable, which are at least as large as the MCIDs previously established, as shown in the following table.

**Table 2. Original study power based on 100 participants in each arm at end of study**

Outcome	MCID*	Power of study to detect MCID	Difference expected based on previous studies	Minimum difference for which study has >80% power
CRQ-SF total	1.0	.99	.73-2.00	0.33
CRQ-SF dyspnea	0.5	.88	.76-1.06	0.45
# of exacerbations	22%	.90	20-26%	20%
6 minute walk test	50 m	.97	48-85 m	25 m

As detailed in section F18 below, we were not able to meet our initial goal of 250 patients and had modify our enrollment goal to 190 patients that, with a 20% attrition, was expected to yield 152 patients at the end of the study. The power for the revised sample size is presented below.

**Table 3. Revised study power based on 76 participants in each arm at end of study**

Outcome	MCID*	Power of study to detect MCID	Difference expected based on previous studies	Minimum difference for which study has >80% power
CRQ-SF total	1.0	.96	.73-2.00	0.45
CRQ-SF dyspnea	0.5	.78	.76-1.06	0.51
# of exacerbations	22%	.81	20-26%	22%
6 minute walk test	50 m	.92	48-85 m	35 m

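### Sample-size Tables 2 and 3: in three rows the MCID, the power at the MCID and the 80%-power minimum difference cannot all hold at one SD (CRQ-SF total in Table 3, 6MWT in both)

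*Protocol*

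**What the plan says.** Section M sets two-sided alpha at 0.05 with target power of at least .80. It assumes 20% attrition and a between-site ICC of 1%. Table 2 is headed "Original study power based on 100 participants in each arm at end of study". After the enrolment goal fell from 250 to 190, Table 3 gives "Revised study power based on 76 participants in each arm at end of study". Both tables have the same columns: MCID, power at the MCID, expected difference, and "Minimum difference for which study has >80% power".

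The rows at issue, in that column order, are:

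- Table 3: "CRQ-SF total 1.0 .96 .73-2.00 0.45"
- Table 3: "6 minute walk test 50 m .92 48-85 m 35 m"
- Table 2: "6 minute walk test 50 m .97 48-85 m 25 m"

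The Table 2 row for CRQ-SF total, "CRQ-SF total 1.0 .99 .73-2.00 0.33", is used for comparison. Section K adds for the walk test: "The MICD for the 6MWT is generally considered to be 25 to 50 meters". It gives no MCID value for CRQ-SF total. No SD or power formula appears in the text, and the note belonging to the asterisk on the MCID column is not in the text available to us.

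**The concern.** An MCID with its power determines the standard error of the group difference, and that standard error determines the difference detectable with 80% power. In three rows the printed minimum difference is well below the value so determined.

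CRQ-SF total is a primary outcome and 6MWT a secondary one. Table 3 is the only statement of revised power in the text available. A reader who wants to know what a null result on CRQ-SF total excludes would get very different answers from the power column and from the minimum-difference column.

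**Working it through.** **Inputs.** Two-sided alpha 0.05 (Section M). Per arm, 100 (250 × 0.8 / 2) and 76 (190 × 0.8 / 2). Row entries from Tables 2 and 3. No SD is needed within a row.

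**Formula.** Let s be the standard error of the difference. Power at difference d is Φ(d/s − 1.960), so the 80%-power difference is d80 = (1.960 + 0.842)s = 2.802s. If MCID M has power P, then M = (1.960 + z_P)s. Hence:

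- d80 = M × 2.802 / (1.960 + z_P)
- P = Φ(2.802 × M/d80 − 1.960)

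The SD, n, ICC design effect and any baseline adjustment enter only through s and cancel within a row. The noncentral t gives the same results to the digits shown.

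**Rows that reproduce.** Dyspnea, Table 2: 0.5 × 2.802/3.135 = 0.447 (printed 0.45). Dyspnea, Table 3: 0.5 × 2.802/2.732 = 0.513 (printed 0.51).

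**Rows that do not.**

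| Row | d80 implied by MCID and power | Printed d80 | Power at MCID implied by printed d80 | Printed power |
|---|---|---|---|---|
| Table 3 CRQ-SF total | 1.0 × 2.802/3.711 = 0.755 | 0.45 | Φ(4.27) > .999 | .96 |
| Table 3 6MWT | 50 × 2.802/3.365 = 41.6 m | 35 m | Φ(2.04) = .979 | .92 |
| Table 2 6MWT | 50 × 2.802/3.841 = 36.5 m | 25 m | Φ(3.64) > .999 | .97 |

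If the MCIDs and powers are right, power at the printed minimum differences is:

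- 0.45 points: Φ(3.711 × 0.45 − 1.960) = 39%
- 35 m (Table 3): Φ(3.365 × 0.70 − 1.960) = 65%
- 25 m (Table 2): Φ(3.841 × 0.50 − 1.960) = 48%

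**Rounding.** Powers of .955–.965 give 0.743–0.766 points. Powers of .915–.925 give 41.2–42.0 m, and .965–.975 give 35.7–37.1 m. Even if 35 m and 25 m were rounded to the nearest 5 m, implied power at 50 m is at least .962 (printed .92) and .999 (printed .97).

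**Check between tables, using only the minimum differences.** At one SD, going from 100 to 76 per arm multiplies d80 by √(100/76) = 1.147 (1.149 with the t distribution).

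- Dyspnea: 0.51/0.45 = 1.13, consistent.
- CRQ-SF total: 0.45/0.33 = 1.36 (1.33–1.40 over rounding), not consistent.
- 6MWT: 35/25 = 1.40 (1.35–1.45 at 1 m rounding, 1.18–1.67 at 5 m), not consistent.

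With the 1% ICC and, as an assumption, seven equal sites, the design effects are 1.28 and 1.21. The expected ratio then falls to about 1.12, further from the printed values.

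**The power column does scale.** At one SD, .99, .88 and .97 at 100 per arm become .962, .78 and .917 at 76 per arm (printed .96, .78, .92). The SDs implied by the MCIDs and powers are nearly constant: 1.64 and 1.65 points, 91.6 and 91.0 m. Those implied by the minimum differences move from 0.83 to 0.98 points and from 63 to 77 m.

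**Could the MCID be the wrong entry?** The tested difference implied by power and minimum difference is d80 × (1.960 + z_P)/2.802:

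- CRQ-SF total: 0.33 × 4.286/2.802 = 0.505 in Table 2 (0.48–0.54 over rounding, if .99 is not a cap) and 0.45 × 3.711/2.802 = 0.596 in Table 3 (0.58–0.61).
- 6MWT: 25 × 3.841/2.802 = 34.3 m in Table 2 (33.0–35.7) and 35 × 3.365/2.802 = 42.0 m in Table 3 (41.0–43.1).

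This reading is live. A difference of 0.5 with 0.33 kept gives powers of .989 and .959 (printed .99 and .96). A difference of 34.5 m with 25 m kept gives .972 and .920 (printed .97 and .92), and 34.5 m lies inside the Section K range. But no single tested difference fits both tables, so a wrong MCID alone does not reconcile them.

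**Revised power (76 per arm) at the low end of the expected ranges, by reading.**

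| Reading | At 0.73 points | At 48 m |
|---|---|---|
| A: MCIDs and powers right | 77% (76–79% over rounding of .96) | 90% |
| B: MCIDs and minimum differences right | 99.5% | 97% |
| C: MCIDs wrong; powers and Table 2 minimum differences right | >99.9% | 99.7% |

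**The case against.** The strongest reply is that the contradiction assumes one SD and one test for both columns of a row, and the protocol states neither. That is correct as a condition. But the dyspnea rows behave exactly as one SD predicts, and nothing in the text says that two were used. If they were, the tables need to say so.

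The Table 2 row for CRQ-SF total is less clear. If .99 is a cap meaning at least .99, the row does not contradict itself. It is therefore not counted among the three, though its 0.33 still does not scale to 0.45.

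The between-table check is weak for 6MWT, because 25 m and 35 m may be rounded to 5 m and the ratio then misses only narrowly. The within-row mismatch carries the point there.

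It is also fair that the correct scaling of the power column makes reading B the least supported. It would need wrong powers that happen to scale correctly, plus an SD that changed in just these two outcomes. This narrows the likely cause to the minimum differences or the MCIDs but does not remove the contradiction.

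Finally, the practical effect is small: enrolment is past, and the dyspnea co-primary, which has the lowest printed power, reproduces. This supports a minor rating.

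**Conclusion.** The point holds, as a minor reporting error. Given one SD and one n per row and two-sided alpha 0.05, three rows contain entries that cannot all be right. Confidence is high for the mismatch and does not extend to its cause, which the documents do not settle.

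The printed sensitivity for CRQ-SF total and 6MWT cannot be relied on. The contrast that matters most is revised power at 0.73 points: about 77%, just under the .80 target, against over 99%. Power at the printed MCIDs stays at or above .92 whichever of the other two columns is right, unless the MCID entries are themselves wrong. Underpowering is not shown. Exacerbations are not used as evidence either way, because that outcome is a count given in whole percents.

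**What to change.** For each outcome, state the SD, the design effect and the difference at which power was computed. Recompute the MCID, power and minimum-difference entries of both tables from that one set of inputs, and correct whichever cells are wrong:

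- **If the MCIDs and powers stand (A):** the minimum differences become about 0.65 points and 36 m in Table 2, and 0.76 points and 42 m in Table 3. The Table 2 value of 0.65 also follows from the Table 3 power of .96 at the same SD (0.755/1.149 ≈ 0.66), so it does not depend on .99 being exact.
- **If the MCIDs and minimum differences stand (B):** power becomes >.99 for CRQ-SF total in both tables. For 6MWT it becomes >.99 in Table 2 and about .98 in Table 3. The change of SD between the tables must then be explained.
- **If the MCID entries are wrong (C):** correct them, reconcile the 6MWT entry with the range in Section K, and restate the minimum differences of one table. These become about 0.38 points and 29 m in Table 3 if the Table 2 values stand, or about 0.39 points and 30 m in Table 2 if the Table 3 values stand.

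While editing, reword the Section M sentence that puts the anticipated differences at or above the MCIDs. The low ends of three expected ranges fall below them (0.73 against 1.0 points, 20% against 22%, 48 m against 50 m).

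The cost is recalculation and wording. Some printed figures may become less favourable. No patients are added and the analysis does not change.
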